3.3.4 Removal of patients from therapy or assessments

3.3.4.1 Removal of individual patients

An excessive withdrawal rate can have a severe negative impact on the scientific value of the trial. Every effort should be made to keep patients in the trial as scheduled. This includes

careful patient selection and appropriate explanation of the trial requirements and procedures prior to enrolment as well as an explanation of the consequences of premature withdrawal.

An individual patient is to be withdrawn from trial treatment if:

- * The patient withdraws consent for trial treatment or trial participation, without the need to justify the decision.
- * The patient develops unequivocal disease progression, supported by radiological evidence where possible.
- * The patient needs to take concomitant drugs that interfere with the investigational product or other trial medication in the opinion of both the investigator and sponsor representative.
- * The patient can no longer be treated with trial medication for other medical reasons (such as surgery, adverse events, other diseases, or pregnancy)
- * The patient has repeatedly shown to be non-compliant with important trial procedures and, in the opinion of both, the investigator and sponsor representative, is not willing or able to stick to the trial requirements in the future. (See [Section 4.3](#))
- * The trial is terminated for any of the reasons listed in [Section 3.3.4.2](#) "Discontinuation of the trial by the sponsor".

Given the patient's agreement, the patient will undergo the procedures for early treatment discontinuation and follow up as outlined in the [Flow Chart](#) (FC) and [Section 6.2.3](#). For all patients the reason for withdrawal (e.g. adverse events) must be recorded in the eCRF. These data will be included in the trial database and reported.

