Archival tumour tissue collection (8)	X											
DNA banking (9)		X										
Tumour assessment and bone scan by RECIST 1.1 (10)							Per institutional practice					
Adverse event	X	X	X	X	X	X	X	X	X	X	X	X
Concomitant therapy	X	X	X	X	X	X		X	X	X	X	X
Abemaciclib dispensation (11)		X				X						
Xentuzumab i.v. (11)		X	X	X	X	X		X	X	X		
Fulvestrant i.m. (11)		X		X		X						
Compliance check abemaciclib (12)						X					X	
Termination of trial medication												X
Completion of the study participation												X

* A 24 h sample is also required at C2V1D2 (see [Appendix 10.2.4](#))

a Screening: The screening visit should be performed within 28 days prior to first drug administration (C1V1). Safety lab at the screening assessment can serve as the C1V1 assessment if performed within 72 hours before the first treatment and does not need to be repeated.

b Treatment courses: All courses are 4 weeks in duration (28 days). All subsequent visit dates should be calculated based on Course 1 Visit 1 date. One or more visits can be skipped in case of treatment interruption. Patients may continue on treatment until the criteria for stopping medication are met (see [Section 3.3.4](#)). A duration of approximately 24 cycles is expected.

c EOTV: End of Treatment visit. If the decision to permanently discontinue all study treatments is taken during a scheduled visit, the End Of Treatment Visit (EOTV) should be performed instead of the scheduled visit (within 7 calendar days after last drug administration)

d FU: All patients should have a follow-up visit 42 days (+7days) after the permanent discontinuation of the study drugs. Patients who have not progressed and not started further treatment at FU should have additional limited follow-up visits at scheduled tumor assessment until progression, start of further anticancer treatment, consent withdrawal, lost to follow-up or death. See [Sections 5.2](#) and [6.2.3](#)

e On course 2 only for PK purposes

f No time window is applicable for course 2 when PK determinations are scheduled for the visit

- * When xentuzumab is discontinued, the visit can be conducted by phone
- 1. Written informed consent must be obtained before any protocol specific screening assessment is performed
- 2. In/Exclusion criteria must be checked at screening and ensured before study medication has been firstly administered

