- 3. Physical exam: includes a thorough cardiopulmonary, abdominal and lymph node exam and an assessment of the mental and neurological status. When xentuzumab is discontinued, physical exam can be done as per institutional practice.
- 4. Vital signs: includes respiratory rate, pulse, temperature and blood pressure. When xentuzumab is discontinued, vital signs assessments can be done as per institutional practice.
- 5. 12-lead ECG: 12-Lead resting electrocardiograms (ECG) are recorded locally and in triplicate. ECG will be performed at Screening, EOTV and FU visit. ECG will be repeated at Visit 1/Day 1, and Visit 3/Day 15 of Course 1, 2, 3; and at Visit 1/Day 1 of Courses 6,9,12, etc. ECG should be performed prior to xentuzumab infusion. . When xentuzumab is discontinued, ECGs can be omitted.
- 6. Safety labs: includes haematology (CBC), coagulation, and negative serum pregnancy test for women with childbearing potential (within 14 days of first study dose) and biochemistry. Urinalysis only at screening and EOTV. Fasting blood test is required for metabolic panels. Baseline Local FSH and estradiol levels should be within 14 days of initial dose of study treatment. See [Section 5.3.3](#) for detail. Safety lab can be performed one day prior to the scheduled test. Unscheduled safety lab should be performed if clinically indicated and documented in the eCRF. . When xentuzumab is discontinued, safety labs can be done as per institutional practice.
- 7. For course 2 only
- 8. Archival tumour tissue collection: the most recent/appropriate archival tumour tissue must be collected prior to the start of trial treatment. Refer to [Appendix 10.3](#) for tissue requirements
- 9. DNA banking: For details please refer to [Section 5.5.1](#).
- 10. Tumour assessments will be performed according to institutional practice. Only the overall response will be collected in the eCRF.
- 11. Abemaciclib, xentuzumab and fulvestrant (in certain countries) should be dispensed through IRT. Patient's screening, all drug dispensation visits and EOTV will be collected in the IRT system
- 12. Compliance check: on Day 1 of every treatment course starting on course 2, and at EOTV

TABLE OF CONTENTS

TITLE PAGE	1
CLINICAL TRIAL PROTOCOL SYNOPSIS	2
FLOW CHART – COHORT A (SOLID TUMOURS).....	14
FLOW CHART – COHORT B (BC TRIPLET WITH LETROZOLE)	16
FLOW CHART – COHORT C (BC TRIPLET WITH ANASTROZOLE)	18
FLOW CHART – COHORT D – DOSE FINDING (BC TRIPLET WITH FULVESTRANT).....	20

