5.2 ASSESSMENT OF EFFICACY

Response Evaluation Criteria in Solid Tumours (RECIST) guideline (version 1.1) ([R09-0262](#)) will be applied as the primary measure for assessment of tumour response, date of disease progression, and as a basis for all protocol guidelines related to disease status (e.g. discontinuation of study therapy). See [Appendix 10.4](#) for details on lesion measurements and response assessment according to RECIST 1.1.

Tumour response will be assessed by Investigator review throughout the study and clinical decisions will be based on Investigator assessment.

Imaging will be performed as indicated in the [Flow Chart](#) and in [Appendix 10.4](#).

Tumour assessment will be assessed per institutional practice. Only the overall response will be collected in the eCRF.

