5.3.6.3 Exemption to (S)AE Reporting

Exempted outcome events are:

- Disease progression
- Malignant neoplasm progression
- Neoplasm progression

Disease Progression is a trial endpoint for analysis of efficacy and as such is exempted from reporting as an (S)AE. Progression of the subject's underlying malignancy will be recorded on the appropriate pages of the (e)CRF as part of efficacy data collection only and will not be reported on the SAE Form. It will therefore not be entered in the safety database (ARISg) and hence not get expeditiously reported. Death due to disease progression is also to be recorded on the appropriate (e)CRF page and not on the SAE Form.

However, when there is evidence suggesting a causal relationship between the study drug(s) and the progression of the underlying malignancy, the event must be reported as an SAE on the SAE Form and on the (e)CRF.

Examples of exempted events of PD may be:

- Progression of underlying malignancy (Progressive disease [PD]): if PD is clearly consistent with the suspected progression of the underlying malignancy as defined by the respective response criteria.
- Hospitalization/Procedures due solely to the progression of underlying malignancy (PD)
- Clinical symptoms and/or signs of progression (without confirmation by objective criteria e.g. imaging, clinical measurement): if the symptom can exclusively be determined to be due to the progression of the underlying malignancy and does meet the expected pattern of progression for the disease under study.

Exempted events are collected and tracked following a protocol-specified monitoring plan. Exempted events will be monitored at appropriate intervals by the Steering Committee.

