6.2.3.2 Follow-up period

All patients must have a follow-up visit 42 days (+7days) after the permanent discontinuation of study drugs.

This follow-up period is aimed for collection of additional AE and PD information. Refer to the [Flow Chart](#) for details.

The follow-up for progression period will end at the earliest if one of the following events is met:

- Lost to follow-up
- Disease progression
- Start of a new anti-cancer therapy
- Death
- End of whole trial as specified in [Section 8.6](#)

Blood samples for soluble biomarkers, PK and ADA must be obtained at this visit. Please refer to [Appendix 10.2](#) for sampling schedule details.

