5.1.3 Cohorts D1 and D2

The primary endpoint for expansion part cohort D1 and D2 is Progression-free survival (PFS) status at 18th month (PFS18).

PFS18 is defined as the PFS status of a patient who is alive without disease progression at 18 months after first treatment administration, where progression is determined according to RECIST 1.1.

PFS is defined as the time from first treatment administration until tumour progression according to RECIST 1.1 or death from any cause, whichever occurs earlier.

Tumour assessments will be performed at screening and then every 8 weeks after start of the first treatment course until week 48 and every 12 weeks thereafter.

For each follow-up imaging time-point an overall tumour response will be determined according to RECIST 1.1. The overall tumour response for each imaging time-point will be selected from the following categories: Complete Response (CR); Partial Response (PR); Stable Disease (SD); Progressive Disease (PD); Non-CR/Non-PD; or Not Evaluable (NE).

For details on the imaging process and RECIST evaluation, see Section 5.2 and Section 10.4 of the CTP.

Derivation of endpoint PFS

Derivations below are described in days. However, the endpoints below will be presented in months in the statistical tables produced for the Clinical Trial Report (CTR).

Proprietary confidential information © 2021 Boehringer Ingelheim International GmbH or one or more of its affiliated companies

For patients with 'event' as an outcome for PFS: (according to RECIST version 1.1)

- PFS [days] = date of outcome - date of the first treatment administration + 1.

For patients with 'censored' as an outcome for PFS: (according to RECIST version 1.1)

- PFS (censored) [days] = date of outcome - date of the first treatment administration + 1.

The censoring rules for PFS (i.e. outcome and date of outcome) are given in [Table 5.1.3:1](#). Clinical disease progression will not be considered for determination of a PFS event, unless the outcome of the progression is death.

If patients would have their radiological examinations over a number of days, i.e. target lesions assessed on day x, non-target lesions assessed on day y and new lesion (if applicable) on day z, the following rules will be applied:

- If the overall response is PD, the earliest date of multiple assessments will be taken.
- If the overall response is SD, Non-CR/Non-PD, PR, CR or NE, the latest of multiple assessment dates will be taken to censor the patients.

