Subsequent anti-cancer therapy started before progression or death	Censored	Date of last radiological assessment before subsequent anti-cancer therapy
No baseline and/or post-baseline imaging and subsequent anti-cancer therapy started prior to a death	Censored	Date of randomisation (or first treatment administration, in non-randomised trials)

In order to identify that consecutive imaging time-points are missing for a given patient, a nominal time point [8, 16, 24, 32, 40, 48, and then every 12 weeks thereafter] will be assigned to each and every image. This is achieved by creating windows for every RECIST assessment. The windows are defined in [Table 6.7.2: 1](#).

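### Clinical progression can end treatment but is censored in the PFS analysis, so the D1/D2 Kaplan-Meier 18-month rate can be biased upward; a sensitivity estimate should stand beside it

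*Protocol*

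**What the plan says.** **Stopping treatment.** Protocol 3.3.4.1 withdraws a patient from treatment if "The patient develops unequivocal disease progression, supported by radiological evidence where possible". It also requires the reason for withdrawal to be recorded in the eCRF. Protocol 5.2 points another way: RECIST 1.1 determines the date of progression and serves "as a basis for all protocol guidelines related to disease status", with discontinuation of study therapy as its example. Protocol 5.3.6.3, on adverse event exemptions, accepts that progression may be recognised from symptoms alone, without imaging.

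**Follow-up.** Protocol 6.2.3.2 says "The follow-up for progression period will end at the earliest if one of the following events is met". Its list includes disease progression and start of a new anti-cancer therapy, and does not say whether progression means RECIST progression. Footnote d of the D1/D2 flow chart is equally open: "Patients who have not progressed and not started further treatment at FU should have additional limited follow-up visits at scheduled tumor assessment until progression". Footnote 10 of the same chart now reads "Tumour assessments will be performed according to institutional practice. Only the overall response will be collected in the eCRF".

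**Analysis.** SAP 5.1.3 states "Clinical disease progression will not be considered for determination of a PFS event, unless the outcome of the progression is death". In SAP Table 5.1.3:1 a living patient without radiological progression is censored at the last scan, or before the gap if two or more consecutive scans were missed. The row "Subsequent anti-cancer therapy started before progression or death" is censored at the last scan before that therapy. Death after no more than one missed scan is an event.

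**Estimator and reference levels.** Protocol 7.3.1 derives the D1/D2 18-month rate by Kaplan-Meier. SAP 7.4.3 gives the number and percentage of treated patients free of progression or death at month 18, and also Kaplan-Meier estimates at 6, 12 and 18 months. Protocol 7.7 illustrates the design with observed rates of 57% (D1) and 65% (D2).

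**The concern.** Kaplan-Meier estimation assumes that a censored patient has the same future risk as those still observed. A patient taken off treatment because the investigator judges the disease to have progressed does not. If no RECIST progression is recorded, and the patient survives or starts another therapy, the rules above remove that patient from the risk set without an event. The censoring is then related to outcome and acts in one direction, raising the estimated 18-month rate.

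D1 and D2 have no control arm in which a similar bias could offset it. The result will naturally be read against the levels in Protocol 7.7, whose probabilities of a false positive signal allow for dropout but not for this kind of censoring.

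**Working it through.** **Inputs.** All from Protocol 7.7: n = 30 per cohort, 20% dropout, D1 true rate 43% against 57%, D2 true rate 52% against 65%. The share c of failures that are clinical only, non-fatal and censored is not in the documents, so it is varied.

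**1. Reproduce the plan's figures.** Take an effective size of 30 × 0.8 = 24 and a normal approximation.
- D1: SE = √(0.43 × 0.57 / 24) = 0.101; (0.57 − 0.43) / 0.101 = 1.39; upper tail 8.3% (stated 8%).
- D2: SE = √(0.52 × 0.48 / 24) = 0.102; (0.65 − 0.52) / 0.102 = 1.27; upper tail 10.1% (stated 10%).

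A Kaplan-Meier simulation of 40,000 trials, with exponential PFS and independent dropout of 20% by month 18, gives 7.6% and 8.8%. At true rates of 60% (D1) and 69% (D2) it gives 62.5% and 67.8% (stated 62% and 68%). The plan's figures therefore reproduce when dropout is unrelated to outcome.

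**2. Effect on the estimate.** Under a constant hazard, censoring a share c of failures leaves a fraction 1 − c of the hazard visible, so Kaplan-Meier estimates S^(1−c). For D1 at c = 10%: 0.43^0.9 = 46.8%. For D2 at c = 10%: 0.52^0.9 = 55.5%. Simulated means agree with the formula.

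**3. Effect on the chance of passing the level (simulated).**

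| c | D1 reads | P(>57%) | D2 reads | P(>65%) |
|---|---|---|---|---|
| 0% | 43.0% | about 8% | 52.0% | about 9% |
| 5% | 44.9% | 11% | 53.7% | 13% |
| 10% | 46.8% | 16% | 55.5% | 17% |
| 20% | 50.9% | 28% | 59.3% | 29% |

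A separate simulation placed the censoring at the preceding scan on the SAP's 8/12-week calendar. It gave nearly the same rates: 44.9%, 46.7% and 50.6% for D1, and 53.6%, 55.3% and 58.8% for D2.

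**4. Allow for deaths.** Suppose 30% of these patients die and are captured as events. The exponent becomes 1 − 0.7c.
- c = 10%: D1 reads 0.43^0.93 = 45.6% and D2 reads 0.52^0.93 = 54.4%; the chances of passing are 12% and 14%.
- c = 20%: D1 reads 0.43^0.86 = 48.4% and D2 reads 0.52^0.86 = 57.0%; the chances are 20% and 21%.

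**5. The crude percentage.** If patients censored before month 18 are not counted as event-free, the expected percentage is S × 0.8: 34.4% for D1 and 41.6% for D2, whatever the value of c. This measure does not rise with c; dropout pulls it down instead.

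**The case against.** The strongest reply is Protocol 5.2. If RECIST governs both the date of progression and discontinuation, then progression in 6.2.3.2 and footnote d means RECIST progression, and a patient with clinical progression only stays in tumour follow-up. A reader might infer from 3.3.4.1 that tumour follow-up stops once clinical progression is declared. The text does not establish that; it leaves two readings open. The flow charts for cohorts B to E also expect an end-of-treatment scan when treatment stops for progression. The current D1/D2 chart has no such line, but institutional practice does not rule out a scan. This part of the reply stands, with one limit: on either reading, new therapy ends follow-up and triggers censoring.

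Second, the SAP follows the protocol's own endpoint, which defines progression by RECIST 1.1. Counting clinical progression answers a somewhat different question. That also stands, and is why the added estimate belongs in a sensitivity analysis.

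Third, the size is assumed. At c = 5% the shift is about 2 points, against a standard error of about 10 points, and fatal cases are partly captured. This stands too.

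Fourth, the crude percentage in SAP 7.4.3 need not rise. That is correct if censored patients are not counted as event-free, but the SAP does not spell out their handling, and the protocol's estimator is Kaplan-Meier.

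**Conclusion.** The D1/D2 Kaplan-Meier 18-month PFS rate can be biased upward. The direction follows from the withdrawal and censoring rules; the size depends on a share the documents do not give. For an assumed share of 5% to 20%, and with none of these patients captured as deaths, the D1 rate rises by about 2 to 8 points and the D2 rate by about 2 to 7. The chance of a false positive signal rises from about 8% to 11–28% in D1 and from about 10% to 13–29% in D2. These figures assume exponential PFS and other dropout unrelated to outcome.

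Three stronger conclusions are tempting but not supported. The reported rate cannot be said to be inflated, since few or no patients may be affected. The plan cannot be said to lack a sensitivity analysis, because parts of the SAP are removed or redacted. And the finding does not justify a rule that a cohort succeeds only if two estimates agree: Protocol 7.2 makes the analyses descriptive with no formal test, and Protocol 7.7 gives illustrative probabilities.

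**What to change.** 1. **SAP 7.4.3.** Keep the RECIST-only Kaplan-Meier rate as primary. Beside it, for D1 and D2 separately, report a sensitivity 18-month rate in which withdrawal for investigator-declared progression is an event on the withdrawal date, unless a RECIST event came earlier. Report how many patients this reclassifies, so that the share assumed above becomes a known figure. Attach no go/no-go rule.
2. **Protocol 3.3.4.1, 5.2, 6.2.3.2 and D1/D2 flow-chart footnote d.** Reconcile what progression means in each place. Which criterion should govern stopping treatment is for the clinical team; the follow-up rule and the analysis need to state which meaning they use.

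**Cost.** The first item is one extra analysis run. It uses the withdrawal reason that Protocol 3.3.4.1 already requires, and assumes that progression can be identified from that field. The reported sensitivity rate may be slightly lower, and it relies on open-label investigator judgement. The second item is a wording change to the protocol, in a trial that Protocol 3.3.4.2 describes as moving towards termination. By itself it would not help patients who switch therapy after clinical progression, so the sensitivity estimate is the more useful of the two.

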3.3.4.2 Discontinuation of the trial by the sponsor

Boehringer Ingelheim reserves the right to discontinue the trial overall or at a particular trial site at any time for the following reasons:

1. Failure to meet expected enrolment goals overall or at a particular trial site
2. Emergence of any efficacy/safety information invalidating the earlier positive benefit-risk-assessment that could significantly affect the continuation of the trial

As described in [Section 2.3](#) Benefit-risk assessment, topline results of 1280-0022 showed no added benefit of xentuzumab compared to placebo when treating participants with metastatic breast cancer. Although xentuzumab treatment was recommended to be discontinued in 1280.18, continuation of treatment of patients with xentuzumab was based on an individual assessment by the investigator. Due to the worsening in benefit-risk, the trial will proceed towards termination based on the following 3 steps:

- a. For xentuzumab-treated patients, the xentuzumab treatment will not extend past the drug expiration date (May 2023) of the last planned GMP manufacturing batch of IMP xentuzumab (provided that all patients are on xentuzumab for at least 2 years when they are tolerating the drug without tumor progression). Patients that will discontinue xentuzumab can still be eligible for continued treatment with abemaciclib and

fulvestrant (standard of care in this setting) provided they are tolerating the drugs without tumor progression.

- b. When all patients have discontinued xentuzumab treatment, if any patient on abemaciclib and fulvestrant is able to continue taking these approved medications off study, then, at the request of the Sponsor, the patient may end such treatment as part of the trial and discontinue study participation (if both the Investigator and patient agree).
- c. After all patients end treatment with all study drugs, the trial will be terminated.

3. Violation of GCP, the CTP, or the contract disturbing the appropriate conduct of the trial

The Investigator / the trial site will be reimbursed for reasonable expenses incurred in case of trial termination (except in case of the third reason).

